4. INVESTIGATIONAL PLAN

4.1. Overall Study Design

This Phase 2/3, multicenter, multinational, open-label study is designed to evaluate the efficacy and safety of daily IV administration of ORGN001 to neonates, infants, and children with MoCD Type A. For the purposes of this study, neonate patients are defined as those from 1 to 28 days of age (inclusive) at the time of first ORGN001 administration, with day 1 of age corresponding to the day of birth. Infants are defined as those from 29 days to < 2 years. Children are defined as those from 2 years to 5 years (inclusive) at the time of informed consent.

Eligible neonates with a prenatal diagnosis of MoCD Type A will undergo Screening/Baseline assessments (eg, brain imaging) prior to or as soon as possible after birth and prior to receiving the first IV infusion of ORGN001. Given the life-threatening and devastating nature of the disease and the potential for a favorable benefit:risk profile for treatment with ORGN001, patients with a prenatal diagnosis may be treated prior to the onset of signs and symptoms associated with MoCD Type A. Additionally, if it is not possible to obtain brain imaging prior to treatment, the priority would be to treat the neonate and obtain brain imaging as soon as feasible afterwards. For those patients, the patient's legal guardians (per country-specific requirements) may be asked to provide informed consent for participation in the study prior to delivery. [REDACTED]

Eligible neonates who do not have a prenatal diagnosis of MoCD Type A but who have the onset of signs and symptoms that may serve as the basis for diagnosis will undergo Screening/Baseline assessments as soon as possible prior to receiving their first daily IV infusion of ORGN001. Data from procedures conducted as part of standard of care prior to study participation may be collected as part of Medical History. Genetic confirmation of the diagnosis of MoCD Type A may be obtained after initiation of ORGN001 therapy.

Eligible patients beyond the neonatal period with genetically confirmed evidence of MoCD Type A, a biochemical profile, and clinical picture consistent with MoCD Type may also be enrolled following completion of Screening/Baseline assessments. Data from procedures conducted as part of standard of care prior to study participation may be collected as part of Medical History. Genetic confirmation of the diagnosis of MoCD Type A may be obtained after initiation of ORGN001 therapy in certain cases.

This study will include a Screening Period, a 12-month Study Period, and a 2-year long-term Treatment Period (Months 13 through 36). Due to the rare nature of the disease and no currently available treatment, patients [REDACTED] may continue to receive study drug until ORGN001 becomes commercially available or development has stopped. For patients receiving ORGN001 past month 36, a safety visit will occur [REDACTED]. Assessments performed during those visits are for the purposes of ongoing safety to receive ORGN001 and may only occur if ORGN001 is not yet commercially available for the patient.

The study will enroll both term and preterm neonates as well as infants and children who meet inclusion and exclusion criteria. In neonates, due to the roles that renal clearance and body weight play in the PK of ORGN001, dosing will be based upon the GA of the patient. Day 1 dosing for term (\geq 37 weeks GA) and preterm neonate (< 37 weeks GA) patients will begin with

[figure not shown]
ORGN001 IV infusions of 700 µg/kg/day and 525 µg/kg/day, respectively. ORGN001 infusions should be administered every 24 hours ± 3 hours apart while hospitalized or at home.

Based on the Investigator and SRC/DMC review of all available data prior to the first (Day 28) dose adjustment, each patient's dose may be initially escalated on or before Day 28, with incremental adjustments up to 1200 µg/kg/day by Month 3. Post administration of the increased dose, patients will undergo an electrocardiogram (ECG) as well as PK sampling. If any dose is not tolerated, the dose will be reduced based on an ad hoc consultation with the SRC/DMC (also see [Section 6.1.2](#) for rules on stopping or delaying dosing).

[REDACTED]
[REDACTED] patients
will [REDACTED] to receive daily infusions of ORGN001 [REDACTED] and will return to the clinic for study visits to assess safety, efficacy, and PK.

Every effort will be made to prevent or, if unavoidable, minimize pain that may occur in association with study-related procedures and assessments. Pain will be monitored as per protocol at each study site and treated appropriately. An alternative blood sampling schedule for infants, for whom less blood volume should be collected, must be used [REDACTED]

Figure 2: Study Design for Study ALXN1101-MCD-202^a

^a Patients who reach 36 months of treatment may continue to receive study drug until ORGN001 becomes commercially available or development has stopped. [REDACTED]

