3.2. Endpoints

Primary Efficacy Endpoint:

- Overall survival (OS)

Secondary Efficacy Endpoints:

- Changes in growth parameters (height, weight, body mass index (BMI), head circumference) through Month 12
- Feeding pattern assessments through Month 12
- Gross Motor Function Classification System Expanded and Revised (GMFCS-E&R) results through Month 12
- Assessments of the Bayley Scales of Infant Development – Third Edition (Bayley-III) Cognitive and Motor Scales as measured through Month 12

- For children aged 3 and above, for whom the Bayley-III is no longer appropriate, the Wechsler Preschool and Primary Scale of Intelligence – Fourth Edition (WPPSI-IV) will be administered.
- For patients with severe developmental delay, the WPPSI may not be an appropriate assessment, and therefore, the Bayley-III may be administered instead.
- Functional ability and activities of daily living, measured by the Pediatric Evaluation of Disability Inventory (PEDI) through Month 12
- Gross Motor Function Measure (GMFM)-88 results through Month 12

[REDACTED]

[REDACTED]

[REDACTED]

Safety Endpoints:

- The type, frequency, severity, timing, and relationship to study drug of any AEs, serious AEs (SAEs), and changes in vital signs, electrocardiograms, and safety laboratory tests

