4.3.7. Electrocardiograms

Electrocardiograms will be collected

Electrocardiograms

should be performed before any blood draws or treatment infusions when those assessments occur at the same study visit.

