5. SCHEDULES OF ASSESSMENTS

The detailed Schedule of Assessments for the initial 12-month Treatment Period and the Schedule for the long-term Treatment Period are provided [REDACTED] [REDACTED].

Table 10: Schedule of Assessments (Screening/Baseline and 12-Month Study Period)

Assessment	Screening / Baseline	12-Month Study Period
Study Day		
Month		
Visit Window (Days)		
Informed consent		
Eligibility		
Demographic data		
Genotype		
Family history		
Medical history		
Physical examination ^b		
Vital signs ^b		
Vital status		
Additional BP measurements ^c		
Chemistry and Hematology ^{b,d}		
Urinalysis ^{b,e}		
Growth parameters		
Feeding pattern		
Neurologic examination ^b		
Modified Glasgow Coma Scale		
Bayley-III (or WPPSI-IV) ^f		
GMFM-88 ^g		
GMFCS-E&R		
PEDI ^h		
Ophthalmologic examination		
Seizure activity ^{b,i}		

Assessment	Screening / Baseline	12-Month Study Period	
Study Day			
Month			
Visit Window (Days)			
Brain MRI ^j			
Brain ultrasound ^k (neonates only)			
ECG ^{b,l}			
EEG ^m			
PD sampling, urine			
PD sampling, blood ^{b,n}			
PK sampling ^{b,o}			
[REDACTED]			
ORGN001 infusion ^p		Daily	
Concomitant medications/procedures ^b	X	Continuous monitoring	
Assess AEs ^b		Continuous monitoring	
Follow-up Visits			

Note regarding blood samples: The total blood volume will not exceed the amount considered acceptable for the patient's clinical condition and the institution's guidelines [REDACTED]. If an Investigator decides to deviate from these limits, the deviation must be fully documented and the Investigator should provide justification for the deviation.

With agreement from the Sponsor, some Baseline assessments may be completed after dosing has begun due to urgency of study drug initiation.

^a For neonate patients born prior to 37 weeks of gestation, the Month 12 assessments will be performed at target time point, adjusted for prematurity by scheduling the visit date plus the addition of the difference between gestational age and full-term gestation of 40 weeks.

^b These assessments will be performed when any dose adjustment occurs: physical examination, vital signs, neurologic examination, ECG, PD sampling (blood), PK sampling, serum chemistry, hematology, urinalysis, evaluation for seizure activity, assessment of concomitant medications, assessment of AEs. Electrocardiograms should be performed prior to any blood draws or treatment administration scheduled for the same study visits.

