^c [REDACTED] additional systolic and diastolic blood pressure measurements are to be collected at approximately 30, 60, 90, and 120 minutes post-EOI, and at 6 and 12 hours post-EOI.

^d Include complete blood count, electrolytes, blood urea nitrogen, creatinine, calcium, alanine aminotransferase, aspartate aminotransferase, alkaline phosphatase, total bilirubin, serum osmolality, and total serum albumin.

^e Include specific gravity, pH, glucose, protein, blood and ketones (by dipstick and microscopic examination), and urine protein to creatinine ratio.

^f The Bayley-III (or WPPSI-IV, as age-appropriate) may be administered within \pm 3 days [REDACTED].

^g Administration of the GMFM-88 must be on the same day as the Bayley-III (or WPPSI-IV).

^h The PEDI must be performed only after completion of the Bayley-III (or WPPSI-IV) and the GMFM-88 at those visits where all 3 assessments are administered

ⁱ The patient's parent/legal guardian will be given a diary to be used to record data regarding the frequency of seizures and any changes in anticonvulsants for the entire duration of the study. The patient's parent/legal guardian will be asked if there has been a presence of seizure activity or any change in seizure activity since the last study visit. Based on a review of the seizure diary as well as observation and review of neurologic examination findings, the Investigator/designee will determine if anticonvulsants, change in medication, or further neuroimaging is warranted.

^j Brain MRI should be obtained prior to the first infusion, where feasible. Completion of a brain MRI may be delayed until after initiation of ORGN001 therapy, if not feasible to complete prior to treatment. Brain MRI will be performed for the identified study visits [REDACTED], if available and if clinical conditions allow. Additional scans may be requested, as needed.

^k For neonate patients, prior to initiation of ORGN001 treatment, a brain ultrasound will be performed in utero and/or after delivery and changes will be assessed over time (through Day 21) at Screening/Baseline and on Days 3 and 21; see also [Section 4.3.11](#).

^l Electrocardiograms should be performed prior to any blood draws or treatment administration scheduled for the same study visits. Electrocardiogram at Screening/Baseline, only if feasible.

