^m Perform EEG for patients with documented or suspected seizure activity at Baseline. Where feasible, a standard EEG [REDACTED] should be performed within 24 hours of first infusion. Subsequent EEGs should be performed in accordance with standard of care.

ⁿ Pharmacodynamic blood sampling will be conducted predose [REDACTED].

^o Pharmacokinetic sampling will be conducted at the EOI \pm 5 minutes, 1 to 2 hours after EOI, and 3 to 4 hours after EOI [REDACTED]. On Day 1 only a pre-dose sample will also be collected.

^p On those days where PK samples are collected, the patient's infusion of ORGN001 must be administered at the study site.

Abbreviations: AEs=adverse events; Bayley-III=Bayley Scales of Infant Development-Third Edition; BP=blood pressure; EEG=electroencephalogram; EOI=end-of-infusion; GMFCS-E&R=Gross Motor Function Classification System Expanded and Revised; GMFM=Gross Motor Function Measure; PD=pharmacodynamics; PEDI=Pediatric Evaluation of Disability Inventory; PK=pharmacokinetics; WPPSI-IV=Wechsler Preschool and Primary Scale of Intelligence – Fourth Edition.

Table 11: Schedule of Assessments (Long-Term Treatment Period and Safety Follow Up)

Assessment	Long-Term Treatment Period				Safety Follow Up/ET Visit ^a
Month					
Visit Window (Days)					
Physical examination					
Vital signs					
Vital status					
Chemistry and Hematology ^b					
Urinalysis ^c					
Growth parameters					
Feeding pattern					
Neurologic examination					
Bayley-III (or WPPSI-IV) ^d					
GMFM-88 ^e					
GMFCS-E&R					
PEDI ^f					
Ophthalmologic examination					
Seizure activity ^g					
Brain MRI					
ECG ^h					
PD sampling, urine					
PD sampling, blood ⁱ					
PK sampling ^j					
ORG001 infusion ^k	↔ Daily ↔				
Assess concomitant medications/procedures	X	X	X	X	X
Assess AEs	X	X	X	X	X

Note regarding blood samples: The total blood volume will not exceed the amount considered acceptable for the patient's clinical condition and the institution's guidelines [REDACTED]. If an Investigator decides to deviate from these limits, the deviation must be fully documented and the Investigator should provide justification for the deviation.

[REDACTED]

^a These assessments will only occur every 6 months for children continuing on ORGN001 past the study follow up period where ORGN001 is not commercially available.

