APPENDIX B. BLOOD SAMPLING VOLUMES TABLES

Table 15: Blood Sampling Volumes (in mL) During the 12-Month Study Period

Sample	Marker or Specific Time	Screening/ Baseline Day ^a -1	
Genotype (if not previously done)			
Serum Chemistry ^b			
Hematology ^b			
Biochemical PD Markers	SSC, [REDACTED]		
	Pre-dose		
	EOI		
ORGN001 PK ^c	1-2 hours after the EOI		
	3-4 hours after the EOI		
[REDACTED]			
Total amount per time point (mL)			

^a Screening/Baseline and Day 1 sampling can be performed on the same day.

^b Chemistry and hematology samples will be assessed [REDACTED]. Capillary samples may be considered if collecting venous samples is not possible.

^c Pharmacokinetic sampling will be performed on the first day of any dose increase.

Abbreviations: EOI=end of infusion; mL=milliliters; PD=pharmacodynamic; PK=pharmacokinetics; SSC=S-sulfocysteine; [REDACTED]

Table 16: Blood Sampling Volumes During the Long-Term Extension Period, After a Dose Adjustment, and at the Safety Follow-up

Sample	Marker or Specific Time	Long-Term Extension Period	Visits after an Unscheduled Dose Adjustment	Safety Follow Up	[REDACTED]
		[REDACTED]	[REDACTED]	[REDACTED]	[REDACTED]
Serum Chemistry ^a		[REDACTED]	[REDACTED]	[REDACTED]	[REDACTED]
Hematology ^a		[REDACTED]	[REDACTED]	[REDACTED]	[REDACTED]
Biochemical PD Markers	SSC, [REDACTED]	[REDACTED]	[REDACTED]	[REDACTED]	[REDACTED]
ORGN001 PK ^b	EOI 1-2 hours after the EOI 3-4 hours after the EOI	[REDACTED]	[REDACTED]	[REDACTED]	[REDACTED]
[REDACTED]		[REDACTED]	[REDACTED]	[REDACTED]	[REDACTED]

^a Chemistry and hematology samples will be assessed [REDACTED]. Capillary samples may be considered if collecting venous samples is not possible.

^b Pharmacokinetic sampling will be performed on the first day of any dose adjustment.

Abbreviations: EOI=end of infusion; mL=milliliters; PD=pharmacodynamic; PK=pharmacokinetics; SSC=S-sulfocysteine; [REDACTED]

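### At a scheduled dose increase, 4.1 puts the ECG after the new dose, while 4.3.7 and Table 10 put a same-visit ECG before it; unless a redacted cell schedules a later ECG, the tracing can miss the new dose

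*Combined protocol and SAP*

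**What the plan says.** Section 4.1 describes scheduled escalation: a first increase on or before Day 28, then further steps up to 1200 µg/kg/day by Month 3. It then states: "Post administration of the increased dose, patients will undergo an electrocardiogram (ECG) as well as PK sampling". It does not name the day.

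Section 4.3.7 says that ECGs "should be performed before any blood draws or treatment infusions when those assessments occur at the same study visit". Its list of ECG occasions is not readable.

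Table 10 footnote b first lists what is done at a dose change: "These assessments will be performed when any dose adjustment occurs: physical examination, vital signs, neurologic examination, ECG, PD sampling (blood), PK sampling", followed by further items. It then gives the order: "Electrocardiograms should be performed prior to any blood draws or treatment administration scheduled for the same study visits". Footnote l repeats that order, and its only visible qualification concerns feasibility at Screening/Baseline.

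Two other notes bear on the day and place. Table 15 footnote c (Appendix B) says: "Pharmacokinetic sampling will be performed on the first day of any dose increase". Table 10 footnote p says: "On those days where PK samples are collected, the patient's infusion of ORGN001 must be administered at the study site".

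On use of the data, the safety endpoints in 3.2 include "changes in vital signs, electrocardiograms, and safety laboratory tests". Section 14.8.4 plans only a listing of ECG results.

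**The concern.** The ECG in 4.1 sits between the increase and the sentence on reducing a dose that is not tolerated, so its evident purpose is to look at the patient on the higher dose. If the general order is applied at that visit, the tracing comes before the first infusion at the new level. It then describes the previous dose and cannot be read against the PK samples drawn after that infusion.

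With about 10 centres in several countries, some may follow 4.1 and others the Table 10 footnotes. The listing could then hold pre-infusion and post-infusion tracings for the same nominal visit, and no visible text requires it to distinguish them. A reader could take an old-dose tracing as evidence about the new dose.

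**Working it through.** No sample size, power or error rate is involved. The check is a comparison of texts, plus simple arithmetic on dose steps and timing.

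**Do the texts describe one visit?**

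1. 4.1 pairs the ECG with PK sampling, both after the increased dose.
2. Table 15 footnote c puts PK sampling on the first day of an increase.
3. Table 10 footnote p has the infusion given at the site on PK days.
4. Table 10 footnote b places ECG, PD blood and PK together at the dose adjustment.

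The natural reading is therefore a single visit with ECG, infusion and PK.

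**What order follows?**

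- By 4.3.7 and footnotes b and l: ECG, blood draws, increased infusion, PK draws. Footnote n has PD blood taken before dosing (its visit list is redacted), so where PD blood is drawn, an ECG ahead of any draw is also ahead of the infusion.
- By 4.1: increased infusion, then ECG and PK.

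One ECG at that visit cannot satisfy both, and no readable text exempts the escalation ECG.

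**Dose step absent from a pre-infusion tracing** (Table 9, µg/kg/day; relative step = increase ÷ previous dose):

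| Group | Time | Step | Relative |
|---|---|---|---|
| Term neonates, infants, children | Day 28 | 1000 − 700 = 300 | 300/700 = 43% |
| Term neonates, infants, children | Month 3 | 1200 − 1000 = 200 | 200/1000 = 20% |
| Preterm neonates | Day 28 | 900 − 525 = 375 | 375/525 = 71% |
| Preterm neonates | Month 3 | 1200 − 900 = 300 | 300/900 = 33% |

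**Is there room for an ECG after the infusion?** The first PK draw is at end of infusion (EOI) ± 5 minutes and the next is 1 to 2 hours after EOI. The gap runs from EOI + 5 to EOI + 60, so 60 − 5 = 55 minutes. Table 10 footnote c adds a constraint on days that are redacted: "additional systolic and diastolic blood pressure measurements are to be collected at approximately 30, 60, 90, and 120 minutes post-EOI". If those readings fall on the same day, the gap splits into 30 − 5 = 25 minutes and 60 − 30 = 30 minutes. About 40 to 50 minutes after EOI would fit, but this is only an example. It comes from the draw times, and the documents give no pharmacological reason for it.

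**The case against.** The strongest reply is redaction. The ECG occasions in 4.3.7 and the ECG cells of Table 10 are withheld. The 4.3.7 entry in the Amendment 3 to Amendment 4 change table shows that a list of occasions exists, with its middle blacked out. A later ECG on the new dose may be scheduled there. Because 4.1 names no day, an ECG at a later visit, taken before that day's infusion, would satisfy both texts. The footnote b ECG could also be a pre-dose tracing with the 4.1 ECG as a second one, since nothing says there is only one. This stands as a condition on the conclusion. It does not remove the point, because the order rule is legible in three places, footnote b speaks to dose adjustments, and 4.1 does not identify any later visit.

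Second, 4.1 is specific and worded *will*, while the order rule is general and worded *should*, so a site could reasonably let 4.1 govern. That is true, but staff working from Table 10 would meet the opposite instruction attached to dose adjustments.

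Third, the consequence is small and a pre-dose tracing has value as a reference, given that the endpoint concerns changes. Both parts stand and are reflected in the verdict and the cost.

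A reader might infer more: that the trial has no ECG on an escalated dose, that a cardiac effect would be missed, or that dose decisions are compromised. The documents do not support this. The schedule is withheld, not shown to be empty. An ECG at any later visit would be recorded on the new dose. The visible criteria for changing doses (2.5, 6.1.1, 6.1.2) contain no ECG threshold. Nothing visible allows an ECG effect to be estimated.

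**Conclusion.** The point holds conditionally. On the visible text, 4.1 and the Table 10 footnotes give opposite orders for the ECG at a scheduled increase. Unless a redacted cell puts the 4.1 ECG at a later visit, a site that follows the footnotes obtains a tracing that does not reflect the new dose.

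The scope is safety tracings at up to two scheduled increases per patient, assuming Table 9 is followed and one ECG is taken at that visit. The tabulated percentages describe the dose difference and do not measure any harm. There is no effect on overall survival, on any ECG summary (ECGs are only listed) or on any visible dose rule. It is a minor, inexpensive improvement to safety data, and confidence is medium because of the redaction.

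As a side note, the ECG row of Table 12 allows any time during the visit while its footnote f puts the ECG first. That table covers unscheduled changes, including decreases (6.1.1), so it does not clearly conflict with 4.1.

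**What to change.** Add an exception to 4.3.7 and to Table 10 footnotes b and l: on the first day of a scheduled dose increase, the ECG required by 4.1 is done after the end of infusion, in a window the sponsor sets around the PK draws and any blood pressure readings due that day. Keep the ECG-first order at all other visits. If a redacted cell already schedules an on-dose ECG at a later visit, name that visit in 4.1 instead.

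In either case, record ECG time relative to infusion and show it in the 14.8.4 listing. When the text is next opened, reconcile the Table 12 ECG row with footnote f.

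The cost is a few lines of wording, one ECG time field if the CRF lacks it, and one listing column. No extra ECG is required. The downside is that this ECG follows some blood draws (any predose PD blood and the EOI PK sample), and staff must fit it between timed procedures. There is also no same-day pre-dose tracing unless the site takes one as well, so tracings from earlier visits serve as the comparison.
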